Secondary aim #1: The quantitative and clinical impacts of OncoFreeze (specifically, on semi-quantitative SUV metrics and on the number of detectable lesions) will be assessed by comparing motion-corrected images derived from OncoFreeze with standard static non-gated PET images and conventionally gated PET images. Two independent readers blinded to the

reconstruction approach will score image quality utilizing a standard Likert-type scale and will extract quantitative metrics (e.g., SUV-max, SUV-peak) for any apparent FDG-avid lesions. Results will be compared for (1) motion-corrected images derived from OncoFreeze, (2) standard static non-gated PET images, and (3) conventionally gated PET images.

Secondary aim #2: The repeatability of dynamic imaging will be evaluated by calculating the measurement agreement and relative differences in semi-quantitative PET metrics between test and retest dynamic images. Imaging metric agreement will be measured using Bland-Altman analysis. Groupwise differences between imaging time-points will also be assessed using t-tests or Mann-Whitney U tests, depending on normality.

Secondary aim #3: The early and late Patlak images (specifically: metabolic rate [slope] and volume of distribution [intercept] images) will be compared in a head-to-head fashion, both qualitatively and quantitatively. This aim will help to determine the optimal post-injection time period for dynamic PET imaging for Patlak analysis.

VIII. Study Risks and Benefits

1) IV Risks:

The risks from IV placement include bruising, pain, or infection at the injection site and possible leaking of IV fluid into nearby tissues. The risk of infection is quite low. There is a moderate risk of pain or bruising. Intravenous injections will be performed only by experienced staff and a physician will be available throughout the procedure in case of any infusion side effects.

2) FDG Risks:

FDG is FDA-approved and known to be very safe. There are few known side-effects associated with FDG. In a large cohort, less than 1% or less of patients experienced transient hypotension, hypo- or hyperglycemia, or transient increases in alkaline phosphatase. The package insert for FDG lists no warnings, interactions, or precautions. A review of the literature reveals no adverse effects.

3) DOTATATE Risks:

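### Secondary aim #2 allows independent-samples tests on paired test-retest scans, and neither aim #1 nor aim #2 says how several lesions per patient enter the analysis

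*Combined protocol and SAP*

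**What the plan says.** All analysis text is in VII. Data Analysis.

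- **Secondary aim #1 (OncoFreeze).** The task of the two blinded readers is set out as follows: they "will extract quantitative metrics (e.g., SUV-max, SUV-peak) for any apparent FDG-avid lesions". The comparison is described only as: "Results will be compared for (1) motion-corrected images derived from OncoFreeze, (2) standard static non-gated PET images, and (3) conventionally gated PET images". No test, model or interval is named. There is no limit on lesions per patient and no per-patient summary.
- **Secondary aim #2 (repeatability).** Repeatability is evaluated by "calculating the measurement agreement and relative differences in semi-quantitative PET metrics between test and retest dynamic images". Then: "Imaging metric agreement will be measured using Bland-Altman analysis". Then: "Groupwise differences between imaging time-points will also be assessed using t-tests or Mann-Whitney U tests, depending on normality". The unit of analysis (lesion, organ or patient) is not stated, nor whether the t-test is paired.

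VI. Methods (Repeatability Cohort Only; Repeat Dynamic Imaging) fixes the design behind aim #2: up to 30 patients, each returning within 7 days for the same procedures. The note in III. Eligibility lets patients with several tracers have dynamic imaging at each procedure but allows only one repeat session per patient.

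**The concern.** There are two separate problems.

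**Pairing.** Test and retest values come from the same patients. Mann-Whitney U compares two independent groups, so it sets the test-retest change against the spread between patients or lesions rather than against the spread of within-patient change. It becomes very insensitive. In a repeatability study that error flatters the method, because a systematic shift between visits that yields a large p-value may be reported as no difference.

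**Clustering.** In aim #1 a patient with 3 lesions gives up to 3 × 2 readers × 3 reconstructions = 18 values per metric. Lesions in one patient share a visit, an injection and an uptake time, so their errors may move together. If every lesion counts as an independent unit, the precision reported is that of the number of lesions, not of the 30 or 75 patients, and patients with many lesions dominate the estimate. Neither aim says how this is to be handled.

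**Working it through.** **1. The plan's own precision figure.** The only interval stated is for the primary aim: 61/75 = 81.3%. The exact (Clopper-Pearson) 95% limits are 70.7% and 89.4%, which round to the stated 71-89%. This is a per-patient proportion, so neither problem touches it. No interval is stated for aim #1 or aim #2.

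**2. Pairing, one value per patient.** Inputs:

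- n = 30 (VI. Methods).
- SD of test-retest differences on the log scale: 0.17/1.96 ≈ 0.087, from the repeatability coefficients of 16.3% and 17.3% in the protocol's background section.
- Assumed, not in the documents: SD between patients 0.5 (log scale) and a true shift of 0.05.

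Standard error of the mean difference:

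- Paired: 0.087/√30 = 0.0159. Shift/SE = 0.05/0.0159 = 3.1.
- Unpaired: the variance of one scan is 0.5² + 0.087²/4 = 0.252, so SE = √(2 × 0.252/30) = 0.130. Shift/SE = 0.05/0.130 = 0.4.

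In 2,000 simulated trials per setting:

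| Setting | Unpaired t | Mann-Whitney U | Paired t on patient means |
|---|---|---|---|
| No shift, 1 lesion | 0% | 0% | 5% |
| Shift 0.05, 1 lesion | 0% | 0% | 86% |
| Shift 0.05, 3 lesions, correlation 0.3 | 0% | 0% | 99% |

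The size depends on the test-retest correlation r, because the unpaired SE exceeds the paired SE by a factor 1/√(1 − r). The inputs above imply r = (0.25 − 0.0019)/(0.25 + 0.0019) = 0.985 and a factor of about 8. With assumed values of r = 0.9 and r = 0.5 the factor is 3.2 and 1.4. The direction is the same for any positive r.

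**3. Clustering, if lesions are pooled as independent.** Let m be lesions per patient and ρ the within-patient correlation of the differences. Both are assumed. The design effect is DE = 1 + (m − 1)ρ, and a nominal 95% interval for the mean difference covers 2Φ(1.96/√DE) − 1.

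| m | ρ | DE | Coverage | Effective n (30 patients) |
|---|---|---|---|---|
| 1 | any | 1.0 | 95% | 30 of 30 |
| 2 | 0.1 to 0.5 | 1.1 to 1.5 | 93.8% to 89.0% | 55 to 40 of 60 |
| 3 | 0.1 to 0.5 | 1.2 to 2.0 | 92.6% to 83.4% | 75 to 45 of 90 |
| 5 | 0.1 to 0.5 | 1.4 to 3.0 | 90.2% to 74.2% | 107 to 50 of 150 |

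For m = 3 and ρ = 0.3: DE = 1 + 2 × 0.3 = 1.6, and coverage = 2Φ(1.96/1.265) − 1 = 87.9%. Over ρ = 0.1 to 0.5, the simulated type I error of a lesion-level paired t-test was 8-18% for m = 3 and 10-25% for m = 5. On patient means it was 5-6%.

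**4. The limits of agreement are less affected.** A limit is the mean plus or minus 1.96 SD, and the SD estimate suffers less from clustering. To a normal approximation, the variance of a limit is understated by [DE + 1.92(1 + (m − 1)ρ²)]/(1 + 1.92), where 1.92 = 1.96²/2. For m = 3, ρ = 0.3 this is (1.6 + 1.92 × 1.18)/2.92 = 1.32, and coverage is 2Φ(1.96/√1.32) − 1 ≈ 91%.

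**The case against.** A reader might infer that the plan commits to treating lesions as independent, so that all intervals and p-values in both aims will be too optimistic. The documents do not support that reading:

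- Aim #1 names no method. Bland-Altman, t-tests and Mann-Whitney U appear only under aim #2. The gap in aim #1 is an unspecified analysis of clustered data, not a wrong test.
- Aim #2 does not mention lesions. With one value per patient there is no clustering. Bland-Altman analysis as worded does not exclude the version for multiple observations per subject.
- The direction is not uniform. Pooled lesion-level paired analyses err towards too much certainty; Mann-Whitney U or an unpaired t-test on these data errs strongly the other way.
- The correlation is unknown and may be modest. VI. Methods asks for about the same dose at retest and for uptake delays to be matched. In aim #1, if the three reconstructions come from one acquisition, as the wording suggests, then dose, uptake time and session largely cancel in within-lesion contrasts and motion is the main shared factor left.

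All of this stands, and it limits the clustering point to a conditional one.

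On pairing, the defence is that the t-test may be meant as paired, and that the Bland-Altman bias estimate would still show a shift. Both are fair. But the Mann-Whitney branch cannot be read as paired, and it is what the plan prescribes when normality fails. A formal test that contradicts the bias estimate beside it serves no purpose.

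**Conclusion.** The pairing defect can be read directly from aim #2 and does not depend on how many lesions a patient has. Mann-Whitney U does not suit test-retest data, and an unpaired t-test fails in the same way. The loss of power is close to total when within-patient variation is small relative to between-patient variation, as it is under the inputs used here; the between-patient SD of 0.5 is an assumption.

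The clustering point is a gap, with a consequence only if lesions are pooled as independent. Its size cannot be fixed from the documents. Over 2 to 5 lesions and correlations of 0.1 to 0.5, a nominal 95% interval for a mean difference covers between 93.8% and 74.2%; at one lesion per patient nothing changes. These figures should not be carried over to the limits of agreement, which are affected less.

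Only secondary aims are touched. The change should be made before the data are analysed, but the primary feasibility conclusion does not depend on it.

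**What to change.** **Aim #2.** State the unit of analysis. Replace the t-test/Mann-Whitney pair with paired methods that treat the patient as the cluster. Either of these will do:

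- a mixed model on log-transformed metrics, with visit as a fixed effect and random effects for patient and lesion within patient; or
- one mean per patient and visit, compared by a paired t-test or Wilcoxon signed-rank test.

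If the model is chosen, let the patient effect differ between visits (a patient-by-visit term). With random intercepts alone, lesion differences within a patient are still treated as independent and the visit contrast keeps the same fault. Report Bland-Altman limits for multiple observations per subject, with intervals from a bootstrap that resamples patients.

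**Aim #1.** Name the analysis. Compare the three reconstructions within lesion using the same clustered model, with reconstruction and reader as fixed effects and a patient-by-reconstruction term for the same reason. State how patients scanned with more than one tracer are counted.

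**Cost.** A paragraph of analysis text and modest programming, with no new patients or scans. Where lesions are correlated, the intervals will be wider than those from pooled lesions, and that width is what the number of patients supports.

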Following the consent process, patients will be escorted to the PET/CT imaging suite where they will be positioned on the imaging bed. As part of the routine clinical PET/CT procedure, an IV will be placed. A low-dose CT will then be performed, followed by the administration of the [clinically-prescribed] radiotracer. Immediately following the tracer administration, PET imaging will begin and continue for approximately 40 - 60 minutes at which point the clinical PET/CT procedure will be performed. Patients will be asked to use the bathroom between the research and clinical imaging.

Specific Dynamic Imaging Procedure

- 1) Upon arrival, patients will be taken to a preparation room where they will be kept warm and they will have time to review the consent form and ask any questions they might have about the dynamic imaging study.
- 2) Patients will be asked to void immediately prior to the start of PET/CT imaging.
- 3) Patients will then be escorted to the scanner and have one IV placed.
- 4) A low-dose CT will be performed.
- 5) A single weight-based dose of a radiotracer will be administered.
- 6) Patients should be positioned comfortably so as to reduce the likelihood of movement during the scan.
- 7) Dynamic PET/CT imaging (utilizing multiple whole-body passes) will begin immediately following the radiotracer injection and will continue until approximately 10 – 20 minutes prior to the start of the clinical scan. These passes will be used to generate early Patlak images.
- 8) Upon completion of the dynamic scan, patients will be asked to use the bathroom to empty their bladders, and then the clinical scan procedure will begin.
- 9) During the clinical scan procedure, patients will wear an Anzai belt, a device that tracks respiratory motion.
- 10) Following the clinical imaging, patients will remain in the scanner for approximately 20 minutes while additional research PET images are

collected. These additional passes will enable the generation of late Patlak images for comparison with early Patlak images.

Repeat Dynamic Imaging

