Risks associated with DOTATATE were assessed in 3 clinical trials and no serious adverse events were reported. In a small percentage of patients, nausea and/or vomiting have been reported following the administration of DOTATATE.

4) Radiation Risks:

This research involves exposure to radiation from PET/CT imaging. As part of the repeatability cohort, patients will receive 1 radiotracer dose (either FDG or DOTATATE) and 3 low-dose CTs as part of the research procedures. The risk from the radiation exposure in this study is too small to be measured. It is not a big risk when compared with other risks you take every day. For more information about radiation exposure, please see the "Radiation Fact Sheet" at <https://hrpo.wustl.edu/participants/radiation-fact-sheet>.

5) PET/CT Imaging Risks:

Patients may experience some discomfort having to lie still for an extended period of time. Patients who dislike small spaces may also find the PET/CT scanner uncomfortable.

IX. Regulatory and Reporting Requirements

The Principal Investigator is responsible for ensuring the safety of subjects who have enrolled in the study. The PI will monitor the study for adverse events directly attributable to participation in this study (i.e. events associated with the additional research PET/CT imaging, not events associated with the clinical PET/CT imaging, including radiopharmaceutical administration). If any breach of confidentiality were to occur, it would be reported according to the HRPO-recommended guidelines.

Reporting

Based on the half-lives of the tracers involved in this study, adverse event tracking will be performed for 24 hours starting at the time of radiotracer administration. Any reported events, anticipated or unanticipated, will be reviewed by the PI and reported per the WUSTL HRPO guidelines. These events will be followed until resolution.

Study deviations will be tracked and recorded throughout the study. Any serious deviations will be reported immediately to the IRB. Otherwise, study deviations will be reviewed by the PI and reported on an annual basis.

X. Data and Safety Monitoring Plan

The principal investigator will review all patient data at least every six months, and provide an annual report to the QASM Committee. This report will include

1. the protocol title, IRB protocol number, and the activation date of the study.
2. the number of patients enrolled to date
3. the date of first and most recent

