patient enrollment 4. a summary of all adverse events regardless of grade and attribution 5. a response evaluation for evaluable patients 6. a summary of any recent literature that may affect the ethics of the study. The study principal investigator and clinical research associate will monitor for serious toxicities on an ongoing basis. Once the principal investigator or clinical research associate becomes aware of a serious adverse event, the SAE will be reported to the HRPO and QASM Committee [add other reporting requirements here if applicable, e.g. sponsor, FDA, collaborating institutions] within 10 working days.

Adverse Events

For the purposes of this protocol, an adverse event (AE) is any untoward medical occurrence within 24 hours of radiotracer administration (e.g., sign, symptom, disease, syndrome, intercurrent illness, abnormal laboratory finding) that emerges or worsens relative to pre-imaging baseline. The Investigators will monitor the occurrence of adverse events during the course of the study. The Investigators need to assess whether there is a reasonable possibility that the study imaging agent caused or contributed to an AE using the following criteria as a guide:

Definite: The adverse event is clearly related to the imaging procedure.

Probable: There is a clinically plausible time sequence between the onset of the AE and administration of imaging tracer. The AE is unlikely to be caused by the concurrent/underlying illness, other drugs, or procedures.

Possible: There is a clinically plausible time sequence between the onset of the AE and administration of imaging tracer, but the AE could also be attributed to the concurrent/underlying disease, other drugs, or procedures.

“Possibly” should be used when the administration of the study imaging tracer is one of several biologically plausible causes of the AE.

Unlikely: The adverse event is doubtfully related to the imaging procedure.

- Not Related: Another cause of the AE is the most plausible and/or a clinically plausible temporal sequence is inconsistent with the onset of the AE and the imaging procedure; and/or a causal relationship is considered biologically implausible.

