If any adverse event is considered to be definitely, possibly or probably related to the investigational imaging tracer, that event will be followed until resolution or until it is deemed chronic or irreversible by the Investigator. If an event is unlikely or not related to the investigational imaging tracer, the event will not be reported.

All adverse effects will be documented and recorded in the medical record and will include:

- Specific reaction according to NCI Common Toxicity Criteria, version 4.0.
- Duration of the reaction
- Severity/grade according to NCI Common Toxicity Criteria, version 4.0. If the adverse event is not addressed by the Common Toxicity Criteria, the severity should be rated as mild (grade 1), moderate (grade 2), severe (grade 3), or life threatening (grade 4).
- Relation of reaction to study agent
- Management of reaction, including any interruption or dose modification of the study drugs.

Event Types

The term “adverse event” is defined in the International Conference on Harmonization Guideline for Good Clinical Practice as follows:

“Any untoward medical occurrence in a patient or clinical investigation subject administered a pharmaceutical product and which does not necessarily have a causal relationship with this treatment. An adverse event (AE) can therefore be any unfavorable and unintended sign (including an abnormal laboratory finding), symptom, or disease temporally associated with the use of a medicinal (investigational) product whether or not related to the medicinal (investigational) product”.

Medical conditions of a subject that exist prior to receiving the investigational imaging tracer will be recorded as medical history. After administration of the investigational imaging tracer, all new medical conditions are considered adverse events. Adverse events occurring in this trial will be recorded in data collection forms, regardless of whether or not they are thought to be associated with the investigational imaging tracer throughout the study period (From the time of consent until the completion of the repeat PET/MR scan). However, the Investigator also will assess the possible relationship between the adverse event and the investigational imaging tracer.

Serious Adverse Events

Any adverse drug experience, occurring at any dose that results in any of the following:

- Death

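### Sections IX and X contradict each other on when adverse events are collected, against which baseline, and which are reported, so harms from the study's own procedures are not reliably captured

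*Combined protocol and SAP*

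**What the plan says.** **Collection period.** Section IX (Reporting) says that "adverse event tracking will be performed for 24 hours starting at the time of radiotracer administration" and gives as its reason "Based on the half-lives of the tracers involved in this study", without stating any half-life. Section X (Adverse Events) builds the same limit into its definition: "an adverse event (AE) is any untoward medical occurrence within 24 hours of radiotracer administration". Section X (Event Types) sets a different period, from consent to the end of the repeat scan (which it calls PET/MR, although the study uses PET/CT).

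**Baseline.** The definition in Section X counts an occurrence "that emerges or worsens relative to pre-imaging baseline". Event Types uses the tracer as the dividing line: "Medical conditions of a subject that exist prior to receiving the investigational imaging tracer will be recorded as medical history". It then adds: "After administration of the investigational imaging tracer, all new medical conditions are considered adverse events".

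**Reporting.** The annual report in Section X is to summarise all events of any grade and cause. Later in the same section, events judged unlikely or not related to the tracer are to be left unreported.

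**Procedures and named risks.** Under Study Procedures in Section VI the IV comes first. Then: "A low-dose CT will then be performed, followed by the administration of the [clinically-prescribed] radiotracer". Section VIII says: "The risks from IV placement include bruising, pain, or infection at the injection site and possible leaking of IV fluid into nearby tissues". At the first visit the IV is described as part of the routine clinical procedure, and Section IX limits the investigator's monitoring to the additional research imaging. The repeat visit, within 7 days, is wholly a research visit (Section VI, Repeat Dynamic Imaging).

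**The concern.** Two kinds of procedural harm sit at the edges of the 24-hour window. The research CT, and at the repeat visit the IV as well, come before the tracer and so before the window opens. An IV-site infection may show itself after the window has closed. Neither kind depends on how fast the tracer decays, so half-life is no basis for a window that must also cover them.

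If site staff apply the Section IX window and the medical-history sentence, such events may be filed as pre-existing or not collected. If they apply the consent-to-repeat-scan period, many of them are collected. The record then depends on which paragraph the person completing the form has read. The investigator's review at least every six months and the annual report could understate the burden of the study's own procedures, and no reader of the report could tell.

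**Working it through.** The plan gives no figure to reproduce, so the check sets the rules against the order of procedures. Let time zero be the tracer injection at the first visit, and let T2 be the injection at the repeat visit.

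**Inputs**
- Window A (Section IX and the Section X definition): 24 h from injection.
- Period B (Section X, Event Types): consent to the end of the repeat scan.
- Repeat visit: within 7 days, which is 7 × 24 h = 168 h (Section VI).
- Subjects: 75 recruited for the multiparametric portion (Section VII), and up to 30 asked to return (Section VI).

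**Size of the disagreement after the first visit.** Period B can run to about 168 h and Window A stops at 24 h. So up to 168 − 24 = 144 h lie inside one period and outside the other. The time from consent to injection is also inside B and outside A.

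**Subjects with no repeat scan.** Period B ends at an event that never happens for them, so its end is undefined. If the up to 30 returning patients are drawn from the 75, this applies to at least 75 − 30 = 45 subjects.

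**Four events put through the rules**

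| Event | Window A | Period B | Baseline rules |
|---|---|---|---|
| Distress during the research CT, first visit | Before the window under Section IX | Inside | New against the pre-imaging baseline, but history under the pre-tracer sentence |
| IV-site infection at 72 h after the first visit, patient returns on day 7 | Outside | Inside | New under the post-tracer sentence |
| Bruise at IV placement, repeat visit | Before T2, so outside that visit's window | Inside | Can count as new, because it follows the first tracer dose |
| IV-site infection more than 24 h after T2 | Outside | Outside | New under the post-tracer sentence, but no period in which to record it |

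The last row assumes that the repeat scan ends less than 24 h after T2. The visit repeats the first-visit procedures: 40 to 60 minutes of dynamic imaging, a scan equivalent to the clinical one, and about 20 minutes more. Window A therefore closes later than Period B, and both have closed when the infection appears.

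**Reporting.** An IV-site infection or distress in the CT would ordinarily be judged unlikely to be due to the tracer. Such an event belongs in the annual summary under one paragraph of Section X and is barred from reporting under another. The causality scale does not settle this. Its definite and unlikely grades refer to the imaging procedure, while its probable and possible grades turn on the tracer.

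**The case against.** A reader might infer that IV and CT events before injection simply become medical history, and that a later site infection can never be an adverse event. The documents do not support that reading, for these reasons.

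- The paragraph with the medical-history sentence goes on to count all new conditions after the tracer, with no 24-hour limit, and to record events from consent onward. Consent precedes the IV and the CT.
- The Section X definition uses a pre-imaging baseline. The research CT is imaging, so distress during it is new. Its wording on 24 hours does not by itself exclude the minutes before injection; only Section IX says that tracking starts there.
- The first-visit IV is a clinical procedure, and Section IX leaves clinical-procedure events out of the investigator's monitoring. It is not a research harm that the plan loses.
- At the repeat visit, the IV and CT follow the first tracer dose, so the post-tracer sentence can already cover them. Nothing says that each injection resets medical history.
- Lying still and disliking small spaces, the imaging discomforts named in Section VIII, continue into the PET after injection.
- Section IX has any reported event reviewed and followed to resolution.

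All of this stands against a claim that procedural events are always excluded. It does not show that they are captured. The same facts that defeat the absolute reading are the contradictions: two periods, two baselines and two reporting rules, with no statement of which governs. The late infection after a repeat visit remains outside both periods. The post-tracer sentence would call it an adverse event, but gives no time in which anyone would look for it or record it.

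**Conclusion.** The point holds as a contradiction within Sections IX and X that leaves capture of procedural harms unreliable, together with one gap that neither recording period covers.

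- **First visit:** the concern is mainly the research CT before injection, which applies to all 75 planned subjects. Events there meet conflicting rules.
- **Repeat visit:** up to 30 visits carry an IV placed only for research. A site infection appearing more than 24 hours after that injection is outside both stated periods.
- **Reporting:** a procedural event that is recorded may still go unreported, depending on which paragraph of Section X is followed.

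The number of events affected cannot be estimated. Section VIII calls the risk of pain or bruising moderate and that of infection quite low, and gives no rates. A claim that the study would report few or no harms therefore goes beyond the documents; what they support is that the safety summary may understate procedural harm. The primary feasibility endpoint is not affected. The verdict assumes that the repeat scan ends within 24 hours of its injection, and that the consent-based period was meant to apply to this study despite naming PET/MR.

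**What to change.** Reconcile Sections IX and X, and the adverse event form, as follows.

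1. State one collection period and one baseline, and delete the competing ones. Both should start no later than the first research procedure of each visit, so that medical history means the patient's status before that procedure and not before the tracer.
2. State when the period ends for subjects who have no repeat scan.
3. Keep a half-life argument, if wanted, for tracer-related events only. For IV-site and other procedural events, set the end on other grounds, name it, and have it extend past the repeat scan.
4. Ask returning patients about events since the first visit.
5. Assess attribution to study procedures as well as to the tracer, using the same terms in every grade of the causality scale.
6. Remove the conflict between leaving events unreported and summarising all events whatever their cause. If the bar is meant only for expedited reports, say so.

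This needs wording changes and no new visit or procedure. The cost is that a few more minor events, such as bruises and IV-site pain, will have to be recorded.
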